5.3.1 Medications to Hold Prior to Study Drug Administration

Since transient hypotension may occur during the rituximab infusion, all subjects taking antihypertensive(s) will be instructed to hold their medication(s) for 12 hours before each infusion in order to decrease the risk of hypotensive events. If a subject has a systolic blood pressure > 180 mm mercury (Hg) or diastolic blood pressure > 100 mmHg at screening, then the antihypertensive(s) will **not** be withheld prior to the infusion. However, it is uncommon for patients with PAH to be hypertensive. Rather, systemic hypotension is more commonly found in this patient group. For hypotensive patients, management will be conducted as outlined in Section 5.4.3.2, *Cardiovascular* and in **Figure 6**.

5.3.2 Preparation for Administration

Appropriate aseptic technique will be used. The necessary amount of rituximab will be withdrawn and diluted to a final concentration of 1 to 4 mg/mL into an infusion bag containing 0.9% Sodium Chloride USP. It is strongly recommended that higher concentrations of rituximab (4 mg/mL) be used for this patient population in order to minimize fluid administration. The bag will be gently inverted to mix the solution, and any unused portion left in the vial will be discarded. Parenteral drug products should be inspected visually for particulate matter and discoloration prior to administration and should not be used if either is present. No incompatibilities between rituximab and polyvinyl chloride or polyethylene bags have been observed.

5.3.3 Pre-medication for Rituximab Infusion

All subjects will receive the following pre-medication prior to each rituximab infusion to prevent hypersensitivity reactions and to reduce the frequency of infusion-related reactions:

- Night before and morning of each study drug infusion:
 - Prednisone 40mg PO (or equivalent)
- Approximately thirty minutes prior to each study drug infusion:
 - Methylprednisolone 100 mg IV (or equivalent).
- Approximately thirty to sixty minutes prior to each study drug infusion:
 - Diphenhydramine 50 mg PO (or equivalent). Dose may be repeated every four hours, as needed.
 - Note: Subjects should be advised that this pre-medication given for the prevention and treatment of infusion-related reactions may cause drowsiness and impairment of driving ability prior to discharge.
 - Acetaminophen 650 mg PO (or equivalent). Dose may be repeated every four hours, as needed.

5.3.4 Administration

RITUXIMAB MUST NOT BE ADMINISTERED AS AN IV PUSH OR BOLUS.

The following administration guidelines should be adhered to:

- Attach the IV administration tubing to the IV bag of prepared rituximab by piercing the bag with the spike end of the tubing.
- Attach the precision regulator extension set to the primary IV administration set.
- Purge all tubing of air by flushing with the prepared solution, allowing only a small amount of solution to be discarded.
- Identify the site for IV access. Prepare for venipuncture per institution standards of practice.
- Introduce the angiocatheter into the vein, and attach to the male port of the precision regulator extension set.

5.3.4.1 Guidance for NYHA Class II or III Subjects

- Open the roller clamp of the IV tubing, and set the precision regulator drip rate to an initial rate of 50 mg/hour.
- Do not mix or dilute rituximab with other drugs.
- If hypersensitivity or infusion-related events do **not** occur, escalate the infusion rate in 50 mg/hour increments every 30 minutes, to a maximum of 400 mg/hour. Subsequent infusions of rituximab can be administered at an initial rate of 100 mg/hour, and increased by 100 mg/hour increments at 30-minute intervals, to a maximum rate of 400 mg/hour as tolerated.

Table 5.1 Rituximab Infusion Rate for First Infusion*

Time (minutes)	Drug per hour (mg/h)	Infusion Rate (mL/h)
0-30	50	12.5
31-60	100	25
61-90	150	37.5
91-120	200	50
121-150	250	62.5
151-180	300	75
181-210	350	87.5
211-240	400	100
241-255	400	100

Note: Advance infusion rate as tolerated

*Based on dilution of rituximab to 4 mg/mL in normal saline

Table 5.2 Rituximab Infusion Rate for Second Infusion*

Time (minutes)	Drug per hour (mg/h)	Infusion Rate (mL/h)
0-30	100	25
31-60	200	50
61-90	300	75
91-120	400	100
121-150	400	100
151-180	400	100
181-210	400	100

Note: Advance infusion rate as tolerated

* Based on dilution of rituximab to 4 mg/mL in normal saline

- Check for extravasation at the infusion site.
- Allow the study medication to infuse until the line of fluid is at the needle insertion site, ensuring that all of the medication is infused.

5.3.4.2 Guidance for NYHA Class IV Subjects

Given the greater concern for potential cardiovascular events related to rituximab administration in this sub-group of subjects, the starting infusion rate and algorithm for titration of rate should be reduced to half of the standard rate outlined in Section 5.3.4.1, *Guidance for NYHA Class II or III Subjects*. Strict adherence to the 30 minute intervals of rate titration will be dependent upon subject tolerability of the infusion.

5.3.5 Criteria for Permanent Discontinuation of Rituximab Infusion

If a subject experiences any of the events listed below, rituximab infusions will be discontinued, and procedures for discontinuation of protocol-specified treatments and follow-up will be implemented (as per Section 3.3.2.1, *Follow-up Requirements for all Treated Subjects*):

- Syndrome resembling tumor lysis syndrome
- NCI-CTCAE Grade 3 (severe) hypersensitivity reaction
- NCI-CTCAE Grade 3 or higher (severe/life-threatening) cytokine release acute infusion reaction
- NCI-CTCAE Grade 3 or higher (severe/life-threatening) cardiac arrhythmias. In addition, see Protocol Section 3.3.2, *Discontinuation of Protocol-Specified Treatment Requirements* for significant cardio-pulmonary disease progression events warranting discontinuation of protocol-specified treatment requirements.
- NCI-CTCAE Grade 3 or higher (severe/life-threatening) mucocutaneous reactions

- Significant hypotension during the infusion not responsive to standard medical intervention
- Events listed in Section 3.3.2, *Discontinuation of Protocol-Specified Treatment Requirements*

5.3.6 Criteria for Withholding Rituximab Infusion

Rituximab infusions are to be withheld if the subject is experiencing any of the following:

- Fever > 38° C
- Symptoms of an upper respiratory infection
- Acute diarrhea
- Signs or symptoms of intercurrent infection or serum sickness such as fever, joint pain, skin rash or hives, hematuria, or hypocomplementemia
- Cytopenia as defined as ANC < 1500/mm³ (or < 1.5 x 10⁹/L), platelets < 100,000/mm³ (or < 100 x 10⁹/L), or hemoglobin < 9.0 g/dL
- Hypotension prior to initiation of infusion

The infusion may be given if a subject has been afebrile for 2 days and has clear lungs. If the subject has been started on antibiotics, the infusion may be given after 2 days, provided cultures are negative. If initiation of rituximab was withheld for hypotension, the subject may return within 3 days for rituximab administration, as long as the return visit is within the windows specified below.

If a subject has a rituximab infusion withheld, the following time windows for infusion will be applicable:

- First Infusion: The first infusion must be given within 7 days of randomization.
- Second Infusion: The infusion must be given 2 – 4 weeks after the first infusion; otherwise the subject will not receive the second infusion.

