contributed to this unusual rate of HACA formation including the low dose of rituximab in the first two dose groups, the use of oral rather than IV steroids as prophylaxis for infusion reactions, and the use of low dose or no immunosuppressive drugs in many of the patients. In summary, while it is possible that recipients of rituximab may develop hypersensitivity, which may extend to other proteins of mouse origin, and thus may not be able to use other chimeric monoclonal antibodies or mouse-derived antibodies in the future, it has not been definitively shown that hypersensitivity to one chimeric molecule precludes someone from receiving another. For additional information on AEs observed to date with study drug and active controls, see the Rituxan Prescribing Information at <http://www.rituxan.com/rituxan/pi>.

Rare serious adverse events (SAEs) have occurred in patients following completion of rituximab infusions: arthritis, disorders of blood vessels (vasculitis and lupus-like syndrome), lung disorders (including pleuritis, scarring of the lung and bronchiolitis obliterans), and eye disorders (uveitis and optic neuritis). Patients with pre-existing cardiac conditions, including arrhythmia and angina pectoris, have had recurrences of these cardiac events during rituximab infusions. Abdominal pain, bowel obstruction, and perforation have been reported in patients receiving rituximab in combination with chemotherapy for malignancy.

Serum sickness, a syndrome consisting of one or more of the following has been reported: fever, joint pain, skin rash or hives, hematuria, or hypocomplementemia. The syndrome may occur as long as several weeks after the first infusion. This syndrome is believed to be caused by deposition in tissues of rituximab-anti-rituximab immune complexes [135-138].

Rituximab is a Category C drug. Reproduction studies in primates at human maternal exposure dose levels showed no teratogenic effects. There are no adequate and well-controlled studies of rituximab in pregnant women. Postmarketing data indicate that B cell depletion can occur in infants exposed in-utero to rituximab, which generally resolves in less than six months. Rituximab has been detected in the serum of infants exposed in-utero.

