5.4.3.6 Serum Sickness

Should serum sickness occur, the infusion will be stopped permanently, and procedures for discontinuation of protocol-specified treatments and follow-up will be implemented (as per Section 3.3.2.1, *Follow-up Requirements for All Treated Subjects*). The subject will be given, if judged clinically appropriate, antihistamines for symptomatic relief of urticaria and nonsteroidal anti-inflammatory drugs for relief of pain. In some cases, a short course of moderate dose corticosteroids may be required for relief of joint pain or fever. If a serum sickness-like reaction occurs, then additional studies will be performed at the time of clinical presentation to evaluate its possible mechanisms. These studies may include measurement of serum cytokines, C3 and C4 levels, a urinalysis, and a skin biopsy with indirect immunofluorescence (if appropriate).

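### Protocol 5.3.6 lets an infusion withheld for signs of serum sickness go ahead after a fever-and-lung check, while 5.4.3.6 stops it permanently

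*Protocol*

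**What the plan says.** Protocol 5.3.6 opens with "Rituximab infusions are to be withheld if the subject is experiencing any of the following". One item on its list is "Signs or symptoms of intercurrent infection or serum sickness such as fever, joint pain, skin rash or hives, hematuria, or hypocomplementemia". After the list comes the general release rule, "The infusion may be given if a subject has been afebrile for 2 days and has clear lungs", followed by separate provisions for subjects on antibiotics and for subjects held because of hypotension. The remaining limit on a withheld second infusion is a window of 2 to 4 weeks after the first; "otherwise the subject will not receive the second infusion".

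Protocol 5.4.3.6 reads: "Should serum sickness occur, the infusion will be stopped permanently, and procedures for discontinuation of protocol-specified treatments and follow-up will be implemented".

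Protocol 1.4 describes serum sickness as any one or more of the signs that 5.3.6 lists, and adds: "The syndrome may occur as long as several weeks after the first infusion".

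Protocol 5.3.5 introduces its permanent-stop list with "If a subject experiences any of the events listed below, rituximab infusions will be discontinued". Serum sickness is not named there, but the last bullet brings in the events of 3.3.2, and 3.3.2 in turn brings in rituximab toxicities under 5.4.3.

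**The concern.** Two sections give different outcomes for what the protocol describes as the same clinical picture. One ends in a possible second infusion, the other in a permanent stop with discontinuation procedures. A site that reads only 5.3.6 finds no pointer to 5.4.3.6. Section 5.3.6 is also where a site is likely to look: the Week 2 visit instructions (6.5.3.2) and footnote 25 of Table 6.1 both cite it for the pre-infusion hematology review, and neither cites 5.4.3.6.

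At stake is whether a masked subject with these signs is re-exposed to study drug, and whether two sites would treat the same presentation alike. Two definitions elsewhere depend on that decision: the per-protocol populations and one of the DSMB triggers.

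**Working it through.** No figure is involved, so the check is a comparison of texts.

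**1. Do the two rules cover the same subjects?** Section 5.3.6 is triggered by signs or symptoms; 5.4.3.6 by serum sickness occurring. Section 1.4 uses the same five signs (fever, rash or hives, painful joints, blood in the urine, low complement) and says one or more of them make up the syndrome. On the protocol's own description, the populations overlap.

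**2. Can it arise before the second infusion?** The second infusion is scheduled for Day 14 ± 4 (6.5.3.2), that is Day 10 to Day 18. If withheld, it may be given 2 to 4 weeks after the first, that is Day 14 to Day 28. Section 1.4 allows onset as late as several weeks after the first infusion. The periods overlap.

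**3. What does each rule do with a given subject?**

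| Presentation after the first infusion | 5.3.6 | 5.4.3.6 |
|---|---|---|
| Fever, rash and hematuria; infusion withheld; then fever-free for 2 days, lungs clear, still within 4 weeks | Release rule met; infusion allowed | If this was serum sickness, permanent stop |
| Rash and joint pain, never febrile, lungs clear | Withhold item present, yet both release conditions are met | If this is serum sickness, permanent stop |

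The second row also shows that the release conditions address only one of the five signs (fever) plus a lung finding. A subject can satisfy them with the other four signs unresolved.

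**4. Is there an exception in 5.3.6?** Hypotension has its own return rule and subjects on antibiotics have a culture condition. Serum sickness has neither.

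**5. What depends on the decision?**
- *Per-protocol sets.* Protocol 8.2.3 and SAP 4.3 (both PP and PP2) require two completed infusions. A subject who is stopped fails both definitions; one who is re-infused can still qualify.
- *DSMB trigger (b)*, Protocol 7.8.2. It counts events that result in permanent discontinuation: 2 of the first 5 subjects, 4 of the first 15, 6 of the first 30, or 8 in total after 30. A stopped subject adds one; a re-infused subject adds none. For a re-infused subject, a related clinical Grade 3 or higher event or a related SAE falls under trigger (d), for which 7.8.2.1 halts enrollment only if the DSMB review is not completed within 2 weeks.
- *Primary analysis population.* Protocol 8.2.2 and SAP 4.2 keep subjects who do not complete therapy, so membership does not change.

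**The case against.** The best defense is that the sections do different jobs. Section 5.3.6 is a day-of-dosing screen for signs that could be infection or serum sickness; 5.4.3.6 applies once serum sickness is established. The release rule is permissive and the stop is mandatory and specific, so a site that follows 5.4.3.6 breaches nothing in 5.3.6. The release rule also reads as if written for infection: applied literally to every listed item it would release cytopenia too, which can hardly have been meant.

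This may well be the intent, but the protocol does not state it. It gives no step that separates suspected from established cases and names nobody to decide. The additional studies in 5.4.3.6 are to explore mechanism, not to settle re-dosing. Section 1.4 works against the distinction, because a single sign may suffice. The objection therefore narrows the problem to wording but leaves the conflict standing.

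The other side is right on three stronger readings that a reader might adopt:
- *That 5.3.5 omits serum sickness, hepatitis B and hematologic malignancy.* It does not name them, but its last bullet leads to 3.3.2, which leads to 5.4.3 and so to 5.4.3.4, 5.4.3.5 and 5.4.3.6. This is indirect, not missing.
- *That labelling a case under one section or the other moves trigger (b).* The trigger counts actual discontinuations against stated denominators. The ambiguity can reach it only by changing what is done. Protocol 8.1 records 30 subjects enrolled by May 2014, so for later subjects the threshold of 8 is the relevant one. Trigger (d) and ad hoc DSMB review remain available.
- *That the second infusion is planned for 2 to 4 weeks.* That window applies only when an infusion was withheld.

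**Conclusion.** The conflict is real. As written, 5.3.6 permits a second infusion for a subject whom 5.4.3.6 bars. It rests on two readings of the text: that the release rule applies to every item on the withhold list that has no rule of its own, and that the description in 1.4 is what sites would use to recognize the syndrome.

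The frequency cannot be given, because the documents state no rate of serum sickness for this population. The size per subject is clear: one of two infusions (1000 mg of a planned 2000 mg), eligibility for both per-protocol populations, and possibly one count towards trigger (b). With 30 subjects per arm, one subject is 1/30 = 3.3% of an arm.

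A reader might infer that the primary result or the power is compromised. The documents do not support that, since non-completers stay in the primary population and no sample-size input depends on this rule. The point is an inconsistency in safety instructions that should be corrected, with a limited effect on secondary analysis sets.

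**What to change.** Reconcile 5.3.6 with 5.4.3.6. In 5.3.6, state whether the release rule applies to suspected serum sickness, to established serum sickness, or to neither, and add a cross-reference to 5.4.3.6. If a distinction between suspected and established cases is intended, say how it is made and by whom. Which rule holds is for the sponsor's clinicians; this review takes no position.

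As a secondary matter of clarity, 5.3.5 could name serum sickness, hepatitis B and hematologic malignancy directly, as it already does for tumor lysis, mucocutaneous reactions and arrhythmia, instead of relying on the chain through 3.3.2.

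The cost is a protocol clarification and a memo to sites. No analysis, sample size or data collection changes.

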5.3.7 Criteria for Temporarily Interrupting and Restarting Rituximab Infusion

The rituximab infusion should be interrupted if the patient develops worsened hypotension or symptomatic bradycardia. SSc-PAH patients may have baseline low blood pressure which the rituximab infusion may exacerbate. Please refer to Section 5.4.3.2, *Cardiovascular* and the Algorithm in **Figure 6** for the suggested treatment of hypotension during rituximab infusions. Sinus bradycardia during rituximab infusion should be quickly responded to as described in Section 5.4.3.2, *Cardiovascular*. If additional measures seem safe and appropriate in order to continue the rituximab infusion, they may be implemented by the clinical site. In all cases, clinical judgment regarding the safety of the individual subject should prevail. If there is adequate response of the bradycardia and/or hypotension and the subject is hemodynamically stable, the infusion may be restarted. The rituximab infusion should be interrupted for NCI-CTCAE Grade 2 or higher cytokine release reactions or Grade 2 hypersensitivity reactions. In most cases, the infusion can be resumed at a 50% reduction in rate (e.g., from 100 mg/hour to 50 mg/hour) when symptoms have completely resolved. Additional treatment with bronchodilators or IV saline may be indicated. Most subjects who

have experienced NCI-CTCAE Grade 2 or less hypersensitivity infusion-related reactions have been able to complete the full course of rituximab therapy. Epinephrine, antihistamines, and corticosteroids should be available for immediate use in the event of an infusion reaction to rituximab (e.g., anaphylaxis). Rituximab therapy should be discontinued in the event of an NCI-CTCAE Grade 3 hypersensitivity or anaphylactic allergic reaction or in the event of an NCI-CTCAE Grade 3 cytokine release acute infusion reaction. Please refer to Section 5.4.3, *Management of Infusion Reactions/Known Toxicities to Rituximab*, for treatment guidelines.

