3.3.2 Discontinuation of Protocol-Specified Treatment Requirements

Protocol-specified requirements for the treatment of subjects, including regimens for investigational, concomitant, or rescue medications, as well as restrictions for disallowed medications, **will** be discontinued for any individual subject under the following conditions:

1. Any protocol-specified treatment requirement will be discontinued immediately at any time during the study at the request of the subject.
2. Investigator or DAIT/NIAID will discontinue any protocol-specified treatment requirement if the subject's health, safety, and/or well-being are threatened.
3. Protocol-specified treatment requirements for rituximab will be discontinued and replaced with appropriate therapy for any subject who experiences any of the following:
 - Significant cardiopulmonary disease **PROGRESSION** as manifested by new or worsening **Grade 3 or higher** AEs including:
 - Incompletely controlled or life threatening arrhythmias
 - Vasovagal episode occurring either during or within 12 hours following an infusion
 - Sinus bradycardia unresponsive to atropine treatment as detailed in Section 5.4.3.2, *Cardiovascular*
 - Chest pain consistent with angina or evidence of myocardial infarction
 - Cardiopulmonary arrest
 - Sustained systemic hypertension requiring additional therapy above baseline medications
 - Sustained hypotension
 - Congestive heart failure worsening from baseline level
 - Pericardial effusion or pericarditis
 - Pneumonitis progressing above baseline level
 - Bronchospasm
 - Dyspnea progressing above baseline level
 - Stridor or other indicators of respiratory compromise
 - New symptomatic pericarditis Grade 2 or higher
 - Toxicities of rituximab, if required as per Sections 5.3.5, *Criteria for Discontinuing Rituximab Infusion* and 5.4.3, *Management of Infusion Reactions/Known Toxicities to Rituximab*
4. Disease progression requiring change in Concurrent Medication as per Section 5.7, *Concurrent Medications and Therapy*.

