5.4.3 Management of Known Toxicities to Rituximab

5.4.3.1 Infusion Reactions (Cytokine release syndrome/acute infusion reaction and Hypersensitivity/Allergic Reaction)

Infusion reactions (cytokine release and/or hypersensitivity reactions) may respond to adjustments in the infusion rate and to medical management. If a general infusion-related

reaction (e.g., fever, chills, myalgia, nausea, headache, rash, mild or moderate mucocutaneous reactions, or symptomatic hypotension) develops, the symptoms will be treated, and the infusion slowed or stopped as warranted. The infusion may be continued at one-half the previous rate once the symptoms have resolved. Hemodynamic fluctuations can have significance for patients with PAH and physicians trained in the care of PAH patients should be available in the event of an infusion reaction. For this reason, patients in this protocol will receive study drug with hemodynamic monitoring as described under Section 5.3, *Administration of Rituximab*. For subjects who experience asymptomatic hypotension, the infusion rate will be temporarily slowed per the investigator's discretion until symptoms resolve.

The rituximab infusion should be interrupted for NCI-CTCAE Grade 2 cytokine release or Grade 2 hypersensitivity reactions. In most cases, the infusion can be resumed at a 50% reduction in rate (e.g., from 100 mg/hour to 50 mg/hour) when symptoms have completely resolved. Treatment of infusion-related symptoms with diphenhydramine and acetaminophen is recommended. Additional treatment with bronchodilators or IV saline may be indicated. Most subjects who have experienced non-life-threatening (NCI-CTCAE Grade 2 or less) hypersensitivity infusion reactions or (NCI-CTCAE Grade 2 or less) cytokine release reactions have been able to complete the full course of rituximab therapy.

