In the event of a NCI-CTCAE Grade 3 (severe) or higher hypersensitivity reaction, or a NCI-CTCAE Grade 3 (severe) or higher cytokine release acute infusion reaction, the infusion should be permanently discontinued and the subject should receive medical treatment. Epinephrine, antihistamines, corticosteroids, albuterol, oxygen, and emergency resuscitation equipment should be kept at the bedside during the infusion of rituximab for immediate use in the event of a hypersensitivity reaction to rituximab (e.g., anaphylaxis). Subjects who experience an NCI-CTCAE Grade 3 (severe) or higher hypersensitivity reaction, or an NCI-CTCAE Grade 3 (severe) or higher cytokine release acute infusion reaction will receive no additional rituximab, and procedures for discontinuation of protocol-specified treatments and follow-up will be implemented (as per Section 3.3.2.1, *Follow-up Requirements for All Treated Subjects*). If it is medically indicated, a subject will be hospitalized for infusion-related reactions.

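### Protocol Section 5.3.7 conflicts with Sections 5.3.5 and 5.4.3.1 on the action after a Grade 3 or 4 cytokine release reaction

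*Protocol*

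**What the plan says.** Three protocol sections govern infusion reactions.

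- **Section 5.3.5 (permanent discontinuation)** lists "NCI-CTCAE Grade 3 or higher (severe/life-threatening) cytokine release acute infusion reaction" and, for the other reaction type, "NCI-CTCAE Grade 3 (severe) hypersensitivity reaction". Its last bullet brings in "Events listed in Section 3.3.2". Section 3.3.2 in turn refers back: "Toxicities of rituximab, if required as per Sections 5.3.5", and also to Section 5.4.3.
- **Section 5.3.7 (temporary interruption and restart)** says: "The rituximab infusion should be interrupted for NCI-CTCAE Grade 2 or higher cytokine release reactions or Grade 2 hypersensitivity reactions". The next sentence begins: "In most cases, the infusion can be resumed at a 50% reduction in rate", conditional on full resolution of symptoms. Further down, the section directs discontinuation for Grade 3 hypersensitivity or an anaphylactic reaction, and for Grade 3 cytokine release. It closes by sending the reader to Section 5.4.3 for treatment guidelines.
- **Section 5.4.3.1 (infusion reactions)** says: "The rituximab infusion should be interrupted for NCI-CTCAE Grade 2 cytokine release or Grade 2 hypersensitivity reactions". Its stopping rule opens: "In the event of a NCI-CTCAE Grade 3 (severe) or higher hypersensitivity reaction". The same rule covers cytokine release of Grade 3 or higher, and the action is permanent discontinuation.

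**The concern.** The interruption sentence appears twice in nearly the same words, but in 5.3.7 it has no upper grade limit for cytokine release. The restart sentence after it is not limited to Grade 2 either. Staff who consult 5.3.7 during an infusion could therefore find a route to restart after a reaction for which the other two sections require a permanent stop. Section 5.3 describes Class IV and advanced Class III patients as at high risk of hemodynamic compromise if they have a hypersensitivity reaction, so these rules should be unambiguous.

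The action taken also feeds into monitoring and analysis. DSMB trigger (b) in Section 7.8.2 counts events that end in permanent discontinuation of the infusion. Trigger (d) takes related clinical events of Grade 3 or higher that do not. The same reaction could count toward one trigger at one site and the other trigger at another. Completion of both infusions is also a condition for the per-protocol population (Protocol 8.2.3) and for both per-protocol populations in SAP 4.3.

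**Working it through.** The plan gives no figure to reproduce here. The check sets reaction type and grade against the instructed action in each section.

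| Reaction and grade | 5.3.5 | 5.3.7 | 5.4.3.1 | Result |
|---|---|---|---|---|
| Cytokine release, Grade 2 | not listed | interrupt, may resume | interrupt, may resume | consistent |
| Cytokine release, Grade 3 | permanent stop | interrupt, may resume; also discontinue | permanent stop | 5.3.7 conflicts with itself and with the others |
| Cytokine release, Grade 4 | permanent stop | literally, only interrupt, may resume | permanent stop | direct conflict |
| Hypersensitivity, Grade 2 | not listed | interrupt, may resume | interrupt, may resume | consistent |
| Hypersensitivity, Grade 3 | permanent stop | discontinue | permanent stop | consistent |
| Hypersensitivity, Grade 4 | not named by grade | not named by grade; anaphylactic reactions are a stop | permanent stop | omission, no opposite instruction |

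The Grade 4 cytokine release row follows from two phrases in 5.3.7. The interruption sentence includes every grade from 2 upward. The discontinuation sentence names Grade 3 alone. Grade 4 meets the first and not the second.

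In the 5.3.5 list, the cytokine release, arrhythmia and mucocutaneous bullets all extend to Grade 3 or higher. Of the bullets that give a grade, only hypersensitivity does not. Section 5.4.3.1 does extend it.

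**Link to the halt rules (Sections 7.8.2 and 7.8.2.1).** Trigger (b) is met at two discontinuations among the first five subjects, four among the first 15, six among the first 30, or eight in total once 30 are enrolled. As proportions, the first three are 2/5 = 40%, 4/15 = 26.7% and 6/30 = 20%. One event is 1/2 = 50% of the smallest threshold and 1/8 = 12.5% of the largest. Section 8.1 reports 30 subjects enrolled by May 2014 out of a planned 60, so the limb of eight governs later enrollment. Trigger (b) brings a temporary halt at once. Trigger (d) applies when related events reach 20% of enrolled subjects, and brings a halt only if the emergency review is not finished within two weeks.

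**The case against.** The strongest reply is that the protocol read as a whole is clear enough. Section 5.3.5 is the section devoted to permanent discontinuation, and it covers cytokine release of Grade 3 and above. Section 5.4.3.1 says the same and by itself gives one action per grade from Grade 2 up for both reaction types. Section 5.3.7 points to 5.4.3, allows restart only in most cases, and says clinical judgment on subject safety should prevail. Interrupting an infusion and then discontinuing it are compatible steps, and it would be odd to stop at Grade 3 but permit restart at Grade 4. Section 3.3.2 also lists several Grade 3 or higher cardiopulmonary events, such as bronchospasm and sustained hypotension, that require stopping on their own account.

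Much of this stands. It lowers the chance that a site would act on the literal text of 5.3.7. It does not remove the conflict, because nothing in 5.3.7 says that the other sections take precedence, and its pointer to 5.4.3 is for treatment guidelines.

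A reader might go further and infer that all Grade 3 and 4 infusion reactions are under conflicting instructions. The documents do not support that for hypersensitivity. No section permits restart after Grade 3 or 4 hypersensitivity, Grade 3 is a stop throughout, and the Grade 4 gap is partly covered by the anaphylaxis wording in 5.3.7, by 5.4.3.1 and by the cross-references between 5.3.5 and 3.3.2.

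A reader might also infer that a reaction followed by restart would escape DSMB attention. It would not. If judged related, it counts toward trigger (d), and Section 7.5.1.1 requires 24-hour reporting of related clinical events of Grade 3 or higher. What changes is the halt rule that applies.

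**Conclusion.** The point holds for cytokine release reactions of Grades 3 and 4. Section 5.3.7 gives two instructions for Grade 3, and for Grade 4 its literal text departs from 5.3.5 and 5.4.3.1. For hypersensitivity the finding is only a missing *or higher* in 5.3.5 and 5.3.7.

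The size is that of a wording inconsistency in operative safety rules. With trigger (b) thresholds between two and eight events, one reaction handled differently could decide whether a threshold is reached, but only if the count is already one short and a site has followed 5.3.7 against the other two sections. The documents give neither the frequency of such reactions nor a rate of differing handling, so no probability can be attached. The finding rests on reading 5.3.7 as written. It takes no view on which cut-off is clinically right.

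**What to change.** Reconcile Sections 5.3.5, 5.3.7 and 5.4.3.1 so that each combination of reaction type and grade leads to a single action, stated identically wherever it appears. One way is to hold the mapping in one section as a short table and have the other two refer to it. The restart sentence in 5.3.7 should name the reactions and grades to which it applies, and the hypersensitivity criteria should state explicitly how Grade 4 is handled. The choice of cut-off belongs to the sponsor and its clinical advisers.

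The cost is wording in three protocol sections. No visit, sample size or analysis changes.
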